# 17 INSURANCE AND INDEMNITY

This trial is a clinician-initiated and clinician-led trial sponsored by Sheffield Teaching Hospitals NHS Foundation Trust.

No provision has been made for indemnity in the event of a claim for non-negligent harm. In terms of liability, NHS Trust and Non-Trust Hospitals have a duty of care to patients treated, whether or not the patient is taking part in a clinical trial. Compensation is only available via NHS indemnity in the event of clinical negligence being proven.

#### 18 PUBLICATION POLICY

Results of this trial will be submitted for publication in a peer reviewed journal. The manuscript will be prepared by the Trial Management Group (TMG) and authorship will be determined by mutual agreement. Co-authors will include members of the TMG and PIs recruiting more than 10% of the eligible patients enrolled on the trial. Any secondary publications and presentations prepared by Investigators must be reviewed by the TMG. Manuscripts must be submitted to the TMG in a timely fashion and in advance of being submitted for publication, to allow time for review and resolution of any outstanding issues. Authors must acknowledge that the trial was performed with the support of Sheffield Teaching Hospital NHS Foundation Trust. Intellectual property rights will be addressed in the Clinical Study Site Agreement between Sponsor and site.

# **20 APPENDICES**

# 20.1 Appendix 1 - AIDS Clinical Trials Group Oncology Committee Documentation of Disease and Definitions of Response

### **Documentation of Disease**

Accurate documentation of the number of lesions may be difficult. An estimate only is required: None;  $> 0 \le 10$ ;  $> 10 \le 50$ ; or > 50.

Documentation of tumour-associated oedema and tumour nodularity is also important.

The location of three to five body markers and bi-dimensional measurements where possible, should be drawn on standard body diagrams showing their relationship to body landmarks.

Photographs are an essential part of the evaluation including photographs of uninvolved areas of skin.

# **Evaluation of Response**

### Complete Response (CR):

The absence of any detectable residual disease, including tumour-associated oedema, persisting for at least 4 weeks.

### Partial Response (PR):

A 50% or greater decrease in the number and/or size of previously existing lesions (skin, oral, measurable or evaluable visceral disease) lasting for at least 4 weeks without the appearance of new lesions or the appearance or worsening of tumour-associated oedema or effusions, or an increase of 25% or more in the product of bi-dimensional diameters of any indicator lesion.

A 50% decrease in the sum of the products of perpendicular diameters of bi-dimensionally measurable marker lesions.

Complete flattening of at least 50% of the lesions (i.e., 50% of previously nodular or plaque-like lesions become macules). In those patients with predominantly nodular lesions, flattening to an indurated plaque of 75% or more of the nodules will also be considered a PR.

Whenever possible, responses should be documented with photographs.

Patients with residual tumour-associated oedema or effusion who otherwise meet the criteria for CR will be classified as having a PR.

# Stable disease (SD):

Any response not meeting the criteria for progression or PR.

# **Progressive Disease (PD):**

The appearance of new lesions or new sites of disease.

An increase of 25% or more in the size of previously existing lesions.

A change in the character of 25% of more of the skin or oral lesions from macular to plaque-like or nodular.

The development of new or increasing tumour-associated oedema or effusion also represents disease progression.

(Adapted from Krown, Metroka et al. 1989).

SCART KAPOSI'	'S SAI	RCOMA EVALU			
This form is to be used to evaluate KS at baseline  At baseline identify 5 representative lesions (including oral and visceral lesions) to be reproducibly measured on follow up and indicate their location on the schematic below.  If present visceral disease should be included as at least one representative lesion.					
	Date	d d m m m	BASE y y	LINE ASSESSME	ENT
A	Lesion	Perpendicular Diameters (mm)	Product of Diameters (mm²)	Oed Present? Y/N	Grade? Mild – 1; Mod – 2; Severe - 3
// B // (\	Α	x			
Z C Z	В	x			
and   host	C	x			
	D	x			
	E	x			
		Sum of Products (mm²)		Grade total num	
	*Grad	e number of KS lesions: 0 - Noi 1- >0 : 2 - >1: 3 - >5	≤10 0 ≤50		

Date	d d m m m y y	Cycle#	Complete Response (CR):  The absence of any detectable residual disease, including tumour-associated oedema, persisting for at least 4 weeks.
Lesion	Perpendicular Product of Diameters Diameters (mm) (mm²)		Partial Response (PR):  A 50% or greater decrease in the number of previously existing lesions (skin, oral, measurable or
A	x	Evaluation of Nodularity:	evaluable visceral disease) lasting for at least 4 weeks without the appearance of new lesions or the appearance or worsening of tumour-associated oedema or effusions, or an increase of 25% or more in the product of bi-dimensional diameters of any indicator lesion.
В			A 50% decrease in the sum of the products of the perpendicular diameters of bi-dimensionally measurable marker lesions.
	X		Complete flattening of at least 50% of the lesions (i.e. 50% of previously nodular or plaque-like lesions become macules). In those patients with predominantly nodular lesions, flattening to an indurated plaque of 75% or more of the nodules will also be considered a PR.
С	x	Oedema Evaluation:	Whenever possible, responses should be documented with photographs.  Patients with residual tumour-associated oedema or effusion who otherwise meet the criteria for CR will be classified as having a PR.
D	x		Stable Disease (SD):  Any response not meeting the criteria for progression or PR.
			Progressive Disease (PD):
E	x	Overall Clinical Response:	The appearance of new lesions or new sites of disease An increase of 25% or more in the size of previously existing lesions A change in the character of 25% or more of the skin or oral lesions from macular to plaque-like or
	Sum of Products (mm²)	CR PR	nodular.  The development of new or increasing tumour-associated oedema or effusion also represents disease progression.
	aluation of nodularity (cutaneous lesions only):		
2 -	Greater than or equal to a 50% of raised lesions have the Greater than or equal to a 25% increase in the number None of the above		aseline or best response d to baseline or best response (minimum of 5 raised lesions)

# 20.2 Appendix 2 - WMA Declaration of Helsinki

#### WORLD MEDICAL ASSOCIATION DECLARATION OF HELSINKI

Recommendations guiding physicians

in biomedical research involving human subjects

Adopted by the 18th World Medical Assembly

Helsinki, Finland, June 1964

and amended by the

29th World Medical Assembly, Tokyo, Japan, October 1975

35th World Medical Assembly, Venice, Italy, October 1983

41st World Medical Assembly, Hong Kong, September 1989

and the

48th General Assembly, Somerset West, Republic of South Africa, October 1996

#### INTRODUCTION

It is the mission of the physician to safeguard the health of the people. His or her knowledge and conscience are dedicated to the fulfilment of this mission.

The Declaration of Geneva of the World Medical Association binds the physician with the words, "The Health of my patient will be my first consideration," and the International Code of Medical Ethics declares that, "A physician shall act only in the patient's interest when providing medical care which might have the effect of weakening the physical and mental condition of the patient."

The purpose of biomedical research involving human subjects must be to improve diagnostic, therapeutic and prophylactic procedures and the understanding of the aetiology and pathogenesis of disease.

In current medical practice most diagnostic, therapeutic or prophylactic procedures involve hazards. This applies especially to biomedical research.

Medical progress is based on research which ultimately must rest in part on experimentation involving human subjects.

In the field of biomedical research a fundamental distinction must be recognized between medical research in which the aim is essentially diagnostic or therapeutic for a patient, and medical research, the essential object of which is purely scientific and without implying direct diagnostic or therapeutic value to the person subjected to the research.

Special caution must be exercised in the conduct of research which may affect the environment, and the welfare of animals used for research must be respected.

Because it is essential that the results of laboratory experiments be applied to human beings to further scientific knowledge and to help suffering humanity, the World Medical Association has prepared the following recommendations as a guide to every physician in biomedical research involving human subjects. They should be kept under review in the future. It must be stressed that the standards as drafted are only a guide to physicians all over the world. Physicians are not relieved from criminal, civil and ethical responsibilities under the laws of their own countries.

### I. BASIC PRINCIPLES

- Biomedical research involving human subjects must conform to generally accepted scientific
  principles and should be based on adequately performed laboratory and animal experimentation
  and on a thorough knowledge of the scientific literature.
- The design and performance of each experimental procedure involving human subjects should be clearly formulated in an experimental protocol which should be transmitted for consideration, comment and guidance to a specially appointed committee independent of the investigator and the

sponsor provided that this independent committee is in conformity with the laws and regulations of the country in which the research experiment is performed.

- 3. Biomedical research involving human subjects should be conducted only by scientifically qualified persons and under the supervision of a clinically competent medical person. The responsibility for the human subject must always rest with a medically qualified person and never rest on the subject of the research, even though the subject has given his or her consent.
- 4. Biomedical research involving human subjects cannot legitimately be carried out unless the importance of the objective is in proportion to the inherent risk to the subject.
- 5. Every biomedical research project involving human subjects should be preceded by careful assessment of predictable risks in comparison with foreseeable benefits to the subject or to others. Concern for the interests of the subject must always prevail over the interests of science and society.
- 6. The right of the research subject to safeguard his or her integrity must always be respected. Every precaution should be taken to respect the privacy of the subject and to minimize the impact of the study on the subject's physical and mental integrity and on the personality of the subject.
- 7. Physicians should abstain from engaging in research projects involving human subjects unless they are satisfied that the hazards involved are believed to be predictable. Physicians should cease any investigation if the hazards are found to outweigh the potential benefits.
- 8. In publication of the results of his or her research, the physician is obliged to preserve the accuracy of the results. Reports of experimentation not in accordance with the principles laid down in this Declaration should not be accepted for publication.
- 9. In any research on human beings, each potential subject must be adequately informed of the aims, methods, anticipated benefits and potential hazards of the study and the discomfort it may entail. He or she should be informed that he or she is at liberty to abstain from participation in the study and that he or she is free to withdraw his or her consent to participation at any time. The physician should then obtain the subject's freely-given informed consent, preferably in writing.
- 10. When obtaining informed consent for the research project the physician should be particularly cautious if the subject is in a dependent relationship to him or her or may consent under duress. In that case the informed consent should be obtained by a physician who is not engaged in the investigation and who is completely independent of this official relationship.
- 11. In case of legal incompetence, informed consent should be obtained from the legal guardian in accordance with national legislation. Where physical or mental incapacity makes it impossible to obtain informed consent, or when the subject is a minor, permission from the responsible relative replaces that of the subject in accordance with national legislation. Whenever the minor child is in fact able to give consent, the minor's consent must be obtained in addition to the consent of the minor's legal guardian.
- 12. The research protocol should always contain a statement of the ethical considerations involved and should indicate that the principles enunciated in the present Declaration are complied with.

# II. MEDICAL RESEARCH COMBINED WITH PROFESSIONAL CARE (Clinical Research)

 In the treatment of the sick person, the physician must be free to use a new diagnostic and therapeutic measure, if in his or her judgement it offers hope of saving life, re-establishing health or alleviating suffering.

2. The potential benefits, hazards and discomfort of a new method should be weighed against the advantages of the best current diagnostic and therapeutic methods.

- 3. In any medical study, every patient including those of a control group, if any should be assured of the best proven diagnostic and therapeutic method. This does not exclude the use of inert placebo in studies where no proven diagnostic or therapeutic method exists.
- 4. The refusal of the patient to participate in a study must never interfere with the physician-patient relationship.
- 5. If the physician considers it essential not to obtain informed consent, the specific reasons for this proposal should be stated in the experimental protocol for transmission to the independent committee (I, 2).
- 6. The physician can combine medical research with professional care, the objective being the acquisition of new medical knowledge, only to the extent that medical research is justified by its potential diagnostic or therapeutic value for the patient.

# III. NON-THERAPEUTIC BIOMEDICAL RESEARCH INVOLVING HUMAN SUBJECTS (Non-Clinical Biomedical Research)

- 1. In the purely scientific application of medical research carried out on a human being, it is the duty of the physician to remain the protector of the life and health of that person on whom biomedical research is being carried out.
- 2. The subject should be volunteers either healthy persons or patients for whom the experimental design is not related to the patient's illness.
- 3. The investigator or the investigating team should discontinue the research if in his/her or their judgement it may, if continued, be harmful to the individual.
- 4. In research on man, the interest of science and society should never take precedence over considerations related to the wellbeing of the subject.

# 20.3 Appendix 3 - Definition of Adverse Events

#### **Adverse Event**

Any untoward medical occurrence in a patient or clinical trial subject administered a medicinal product and which does not necessarily have a causal relationship with this treatment.

#### Comment.

An AE can therefore be any unfavourable and unintended sign (including abnormal laboratory findings), symptom or disease temporally associated with the use of an investigational medicinal product, whether or not related to the investigational medicinal product.

#### **Adverse Reaction**

All untoward and unintended responses to an IMP related to any dose administered.

#### Comment:

An AE judged by either the reporting Investigator or Sponsor as having causal relationship to the IMP qualifies as an AR. The expression reasonable causal relationship means to convey in general that there is evidence or argument to suggest a causal relationship.

#### **Serious Adverse Event**

Any untoward medical occurrence or effect that at any dose:

- Results in death
- Is life-threatening\*
- Requires hospitalisation\*\* or prolongation of existing inpatients' hospitalisation
- Results in persistent or significant disability or incapacity
- · Is a congenital anomaly/birth defect
- Or is otherwise considered medically significant by the Investigator\*\*\*

#### Comments:

The term severe is often used to describe the intensity (severity) of a specific event. This is not the same as serious, which is based on patients/event outcome or action criteria.

- \* Life threatening in the definition of an SAE refers to an event in which the patient was at risk of death at the time of the event; it does not refer to an event that hypothetically might have caused death if it were more severe.
- \*\*Hospitalisation is defined as an unplanned, formal inpatient admission, even if the hospitalisation is a precautionary measure for continued observation. Thus hospitalisation for protocol treatment (e.g. line insertion), elective procedures (unless brought forward because of worsening symptoms) or for social reasons (e.g. respite care) are not regarded as an SAE.
- \*\*\* Medical judgment should be exercised in deciding whether an AE is serious in other situations. Important AEs that are not immediately life threatening or do not result in death or hospitalisation but may jeopardise the subject or may require intervention to prevent one of the other outcomes listed in the definition above, should be considered serious.

#### Serious Adverse Reaction

An Adverse Reaction which also meets the definition of a Serious Adverse Event.

# **Suspected Unexpected Serious Adverse Reaction**

A SAR that is unexpected i.e. the nature, or severity of the event is not consistent with the applicable product information.

A SUSAR should meet the definition of an AR, UAR and SAR.

#### **Unexpected Adverse Reaction**

An AR, the nature or severity of which is not consistent with the applicable product information (e.g. Investigator Brochure for an unapproved IMP or (compendium of) Summary of Product Characteristics (SPC) for a licensed product).

When the outcome of an AR is not consistent with the applicable product information the AR should be considered unexpected.

# 20.4 Appendix 4 - Common Toxicity Criteria Gradings

Toxicities will be recorded according to the Common Terminology Criteria for Adverse Events (CTCAE), version 4.0. The full CTCAE document is available on the National Cancer Institute (NCI) website, the following address was correct when this version of the protocol was approved:

http://ctep.cancer.gov/protocolDevelopment/electronic applications/ctc.htm

# 20.5 Appendix 5 – New York Heart Association Classification – Stages of Heart Failure

[figure not shown]
Class	Patient Symptoms
Class I (mild)	No limitation of physical activity. Ordinary physical activity does not cause undue fatigue, palpitation, or dyspnoea (shortness of breath).
Class II (mild)	Slight limitation of physical activity. Comfortable at rest, but ordinary physical activity results in fatigue, palpitation, or dyspnoea.
Class III (moderate)	Marked limitation of physical activity. Comfortable at rest, but less than ordinary activity causes fatigue, palpitation, or dyspnea.
Class IV (severe)	Unable to carry out any physical activity without discomfort. Symptoms of cardiac insufficiency at rest. If any physical activity is undertaken, discomfort is increased.

# 20.6 Appendix 6 - Canadian Cardiovascular Society Grading of Angina Pectoris

Grade	Description		
1	Ordinary physical activity does not cause angina, such as walking and climbing stairs. Angina with strenuous or rapid or prolonged exertion at work or recreation		
II	Slight limitation of ordinary activity. Walking or climbing stairs rapidly, walking uphill, walking or stair climbing after meals, or in cold, or in wind, or under emotional stress, or only during the few hours after awakening. Walking more than two blocks on the level and climbing more than one flight of ordinary stairs at a normal pace and in normal conditions		
III	Marked limitation of ordinary physical activity. Walking one or two blocks on the level and climbing one flight of stairs in normal conditions and at normal pace		
IV	Inability to carry on any physical activity without discomfort, anginal syndrome may be present at rest		

[figure not shown]
# 20.7 Appendix 7 – Guidance for management of patients with a reduction in LVEF

Echo: Echocardiography

LVEF: Left ventricular ejection fraction Version: Final 2.0 28Sept 2012

[figure not shown]
# 20.8 Appendix 8 – Guidance for investigation of patients with new/worsening dyspnoea\* (not considered related to disease under study)

\* Not considered related to disease under study

[figure not shown]
Includes selumetinib

# 20.9 Appendix 9 - Guidance for management of patients with visual symptoms

# 20.10 Appendix 10 – Guidance for management of creatine kinase elevation

[figure not shown]
To reduce possible consequences associated with creatine kinase (creatine phosphokinase, CK) elevation that may be arising from a muscular source, the management guideline described below should be followed:

\* Muscular weakness, pain or tenderness

Version 3.0 12-Sept-2013

# 20.11 Appendix 11 - Guidance for the management of patients with diarrhoea

\*Diarrhoea becomes complicated by associated vomiting or inability to take oral fluids; marked abdominal distension or cramping; bloody stools, fever or symptoms of hypotension

Document version: Final 2.0 28Sept2012

\*\*Consider interruption or delay of combination anticancer agent if applicable

# 20.12 Appendix 12 - Guidance for the management of patients with rash

# Recommendations to start on day 1 of treatment with selumetinib and for the duration of treatment

- Use skin moisturiser (thick, alcohol-free) at bedtime
- Avoid excessive exposure to sunlight
- Use sunglasses/sunscreen (PABA-free, SPF ≥15; UVA and UVB protection) as needed
- Use of topical retinoids or benzoyl peroxide is not recommended

#### **CTC Grade 1 rashes**

Mild or moderate strength topical steroid and/or topical antibiotic

#### CTC Grade 2 rashes

Moderate strength topical steroid and oral antibiotic

# CTC grade ≥3 rashes CTC grade 2 rashes considered by the patient to be intolerable

Moderate strength topical steroid

and oral antibiotic (consider broad spectrum/gram negative cover if infection suspected)

Consider referral to a dermatologist: manage rash per recommendation

Interrupt selumetinib until rash improves to grade 2 or less

Selumetinib may be restarted at original dose or reduced at the discretion of the

Table 1: Example topical steroids and antibiotics (use according to local guidelines)				
Topical steroids moderate strength	Triamcinolone acetonide 0.025% Fluticasone proprionate 0.05%	Desonide 0.05% Aclometasone 0.05%		
Topical antibiotics	Clindamycin 1 - 2%	Erythromycin 1% - 2%		

Metronidazole 1%

Silver sulphadiazine 1%

Oral antibiotics	Doxycycline 100 mg bd mg bd	Minocycline 100 mg bd Oxytetracycline 500

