#### 7.3.5 Management of skin toxicities associated with Selumetinib

Skin toxicities should be graded using CTCAE criteria. Selumetinib dose modifications are defined in section 7.4. Early initiation of treatment for rashes is strongly recommended to minimise the duration and severity of the adverse event. A suggested algorithm for the management of skin rashes is shown in Appendix 12.

Page **26** of **61** 

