# 7.4.1 Haematologic Adverse Events

Grade of	Management/Next Dose for Selumetinib	
Event		
grade 1	No change in dose	
grade 2 No change in dose		
grade 3	Hold* until < grade 2 – resume at 1 dose level lower if indicated**	
	(unless defined as a DLT).	
grade 4 Off protocol therapy		
* Patients requiring a delay of > 2 weeks should go off protocol therapy.		
** Patients requiring > 2 dose reductions should go off protocol therapy.		

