# 7.4.2 Non-Haematologic Adverse Events (including biochemistry/hepatic/renal function)

Grade of	Management/Next Dose for Selumetinib							
Event								
grade 1	no change in dose							
grade 2	Hold until ≤ grade 1∞ – resume at same dose, except for rash where							
	CTCAE grade 2 rash is acceptable							
grade 3	Hold* until < grade 2 – resume at 1 dose level lower if indicated,**							
	except for rash where patients with CTCAE grade 2 rash may restart							
	treatment (unless defined as a DLT).							
grade 4	Off protocol therapy							
								

- \* Patients requiring a delay of > 2 weeks should go off protocol therapy.
- \*\* Patients requiring > 2 dose reductions should go off protocol therapy.
- ∞Please refer to Appendix 10 for management of elevated creatine kinase

7.5 The dose modification algorithm allows for the following dose reductions:

75mg bd  $\rightarrow$  50mg bd  $\rightarrow$  75mg od

returns will be disposed of by Pharmacy according to local hospital practice. Further information can be found in the Pharmacy Manual (supplied separately).

CRCTU

Treatr

at the

es

ug

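### Appendix 12 permits restart after any grade ≥3 rash, including grade 4, which section 7.4.2 takes off protocol therapy, and its release threshold for intolerable grade 2 rash is already met at onset

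*Protocol*

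**What the plan says.** Three parts of the protocol deal with holding and restarting selumetinib for rash.

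- **Appendix 12 (guidance on rash).** The last block is headed "CTC grade ≥3 rashes CTC grade 2 rashes considered by the patient to be intolerable". It tells the site: "Interrupt selumetinib until rash improves to grade 2 or less". It continues: "Selumetinib may be restarted at original dose or reduced at the discretion of the". The end of that sentence is lost in the copy reviewed, and nothing is inferred from the missing words.
- **Section 7.4.2 (non-haematologic events).** The entry in the grade 4 row is "Off protocol therapy". Rash is treated differently from other events in two rows only. In the grade 2 row, "CTCAE grade 2 rash is acceptable", so the general hold to grade 1 does not apply. In the grade 3 row, a patient may restart with rash still at grade 2.
- **Section 7.3.5 (skin toxicities).** This section sets the order of the two texts: "Selumetinib dose modifications are defined in section 7.4". It introduces Appendix 12 as a suggested algorithm.

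Section 7.4 also requires selumetinib to be withheld for any related event that is intolerable, whatever its grade. Next to the withhold rule for related events of grade 3 or above, it notes that they should be reported as DLTs, and it points to section 3.1.1 for the definition.

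**The concern.** A clinician managing a rash is likely to reach for the one-page rash guide. If that guide is used alone, a patient with grade 4 rash that has settled to grade 2 could be put back on selumetinib, possibly at the full dose. Under the table in 7.4.2 the same patient has finished protocol therapy. One patient should not get two answers depending on which page is open.

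The second difficulty is smaller. Grade 2 rash that a patient finds intolerable is to be interrupted until it is grade 2 or less. Judged by grade alone, that condition is true on the day the hold begins, so the threshold does not tell the site when to resume.

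The stakes are the safety of a patient with severe rash and consistent handling across sites. Holds and restarts also feed the dose intensity and number of cycles that section 13.2.2 reports, but those are descriptive summaries.

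**Working it through.** No arithmetic applies. The check sets the texts side by side, one grade of rash at a time, for an event considered related to selumetinib.

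| Rash | Section 7.4 / 7.4.2 | Appendix 12 | Agree? |
|---|---|---|---|
| Grade 2, tolerated | Acceptable; hold to grade 1 not required | Treat; no interruption | Yes |
| Grade 2, intolerable | 7.4: withhold. The 7.4.2 grade 2 row gives no restart level for rash | Interrupt to grade 2 or less | No working release level by grade |
| Grade 3 | Hold; may restart at grade 2, one dose level lower if indicated | Interrupt to grade 2 or less; restart at original or reduced dose | Broadly yes |
| Grade 4 | Off protocol therapy, with no exception for rash | Same as grade 3: restart permitted | **No** |

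**Grade 4.** The appendix heading covers grade 3 and above, and grade 4 falls within that. The hold and the permission to restart are both complete in the visible text. In 7.4.2 the rash exceptions stand in the grade 2 and grade 3 rows, and the grade 4 row has none. The two instructions therefore differ for grade 4.

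**Grade 3.** There is no conflict here. Both texts allow a restart at grade 2, and both leave a dose reduction open. The appendix does not repeat the two-week limit on delay from 7.4.2, but it says nothing against it.

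**Intolerable grade 2.** The appendix threshold is grade 2 or less, and the rash is grade 2 when the hold starts, so no change of grade is needed to satisfy it. The 7.4.2 grade 2 row cannot supply a level, because it exempts rash from the hold to grade 1. Section 7.4 supplies the reason to hold (intolerability), which persists for as long as the rash is intolerable, but it states no restart criterion.

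**DLT note in 7.4.** The grade 3 rows of 7.4.1 and 7.4.2 both apply "unless defined as a DLT". The definition is in 3.1.1, which confines DLTs to cycle 1 of phase I. Section 3.1.2 states that phase I is complete. No new phase II event can meet the definition, so the grade 3 resume rows remain in force in phase II.

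**The case against.** The best defence is that the protocol already ranks the two texts. Section 7.3.5 says that 7.4 defines the dose modifications and calls the appendix only a suggestion. The appendix wording on restart is permissive, so the bar in 7.4.2 still applies to grade 4. This stands as to which text governs: a site that reads 7.3.5, 7.4.2 and the appendix together should take the patient off treatment. It does not remove the mismatch. The appendix issues its own hold and restart instruction, expressly includes grade 4, and does not refer back to 7.4.2 at that point. The rule in 7.4 for conflicting recommendations concerns a patient with several adverse events, not two texts about one event.

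On intolerable grade 2 rash, a reader might infer that the appendix lets a site end the hold at once. The document does not support that. The instruction speaks of the rash improving, which an unchanged rash has not done. Section 7.4 independently requires withholding while an event is intolerable, so an immediate restart would breach it. What remains is a threshold that does no work, which is a matter of drafting.

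A reader might also infer that the DLT note in 7.4 turns every related grade 3 event in phase II into a DLT and so removes it from the resume rule. That is largely answered by the pointer to 3.1.1 in the same sentence, which brings in the limit to cycle 1 of phase I. At most, a phase II site makes an unnecessary DLT report.

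**Conclusion.** The point holds as a minor inconsistency in safety wording. Its core is grade 4 rash, where Appendix 12 permits a restart and 7.4.2 does not. The secondary point is that the grade-based release level for intolerable grade 2 rash is already met at onset, with 7.4 still holding the drug while the rash is intolerable.

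The size cannot be given. Section 7.3.1 reports treatment-related rash of at least grade 3 in 9% of patients in other selumetinib studies. The protocol does not say how much of that was grade 4, and it gives no rate for intolerable grade 2 rash. The 9% therefore indicates how often the appendix block might be used, not how often the conflict would arise, and it should not be turned into an expected number of affected patients.

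A reader might go further and suspect that the results are compromised. Nothing in the document shows this. The 75 mg bd dose was fixed in phase I under 3.1.1 and 3.1.2. The primary endpoint, best objective response to the end of cycle 6, and the error rates of the two-stage design do not depend on this wording.

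The conclusion rests on the visible text of the appendix. If the lost end of the restart sentence, or a part of the flow chart not shown, excludes grade 4, the main point falls away.

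**What to change.** In Appendix 12:

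1. Limit the restart instruction to grade 3 rash, and state that grade 4 rash goes off protocol therapy in line with section 7.4.2.
2. For intolerable grade 2 rash, replace the release threshold with: until tolerable or grade ≤1.

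Optional tidy-up in section 7.4: add to the DLT reporting note that it applies to phase I, cycle 1 only, leaving the rule to withhold for all related events of grade 3 or above as it is.

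The cost is a few words in an amendment. No extra data, visits or analyses are needed.
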